11.3.3 Missed Dialyses

Only missed dialyses (defined as a dialysis session that was planned but not received at the patient's usual outpatient dialysis center) with starting dates that occur during the Treatment Period and up to 7 days after the last study medication date will be taken into account. The days of missed dialysis will be calculated as the sum of all missed dialyses in days (# of missed dialysis/weekly prescribed dialysis frequency* 7), where weekly prescribed dialysis is TIW in this study.

The following missed dialysis-related data will be analyzed and compared between the 2 treatment groups:

- Occurrence (number) of missed dialyses. The number of missed dialysis for each subject will be collected. The mean number of missed dialysis will be analyzed and compared between the 2 treatment groups using the Mantel-Haenszel mean score test adjusting for stratification factors.
- Proportion of subjects who has missed dialyses. The proportion of subjects with missed dialysis will be compared between the 2 treatment groups using CMH model adjusting for stratification factors.
- Number of days of missed dialyses per subject-exposure year (PEY). The number of days of Missed Dialysis for each subject will be calculated. The mean number of days of Missed Dialysis will be analyzed and compared between the 2 treatment groups using the Mantel-Haenszel mean score test adjusting for stratification factors.

11.3.3.1 Red Blood Cell Transfusion

For a subject receiving RBC or whole blood transfusion, the Time at Risk (time up to first use) will be calculated (in years) as:

$$(\text{First use of transfusion date} - \text{First dose date of study medication} + 1) / 365.25$$

For a subject not receiving transfusion, the Time at Risk (time until they get censored) is calculated as:

$$(\text{Date of last study medication} - \text{First dose date of study medication} + 1) / 365.25$$

The red blood cell transfusion form of the eCRF in the cumulative visit will be used to derive the number of RBC packs. The number of RBC units is collected in this form. For transfusions where the number of units is not given but the volume transfused is given, the number of units will be estimated by dividing the volume transfused by 250 mL (for transfusion of packed cells) or by dividing the volume transfused by 500 mL (for transfusion of whole blood).

The total number of RBC units/packs during the Treatment Period is calculated for each subject by the sum of the transfused units between the Analysis Date of First Dose and up to the Analysis Date of Last Dose. The following 2 endpoints will be analyzed:

- Proportion of subjects who receive RBC transfusions. The proportion of subjects who received RBC transfusion will be compared between the 2 treatments using logistic regression model adjusting for baseline hemoglobin as covariate and treatment group and stratification factors as fixed effects.
- Number of RBC packs per subject-month exposure to study medication. The mean number of RBC packs will be compared between the 2 treatment groups using ANCOVA model adjusting for baseline hemoglobin as covariate, treatment group, and stratification factors as fixed effects.

11.3.3.2 ESA Usage in roxadustat patients

For roxadustat subjects, ESA use will be recorded in the CRFs. The total number of ESA-week dose per subject will be calculated and listed.

When ESA dose were needed in the EPO arm, such dose will be captured as dose change of study drug. If another ESA were used in addition, it too will be summarized separately from roxadustat patients.

For each entry that meets the criteria below the ESA-week will be calculated as follows:

- If drug is epoetin alfa, epoetin beta, or an epoetin biosimilar (ATC code: B03XA01), then $\text{ESA-Weeks} = (\text{stop date} - \text{start date} + 1) / 7$;
- If drug is darbepoetin SQ or IV dose (ATC code: B03XA02), then $\text{ESA-Weeks} = 2 \times (\text{stop date} - \text{start date} + 1) / 7$;
- If drug is Mircera IV or SQ dose (ATC code: B03XA03), then $\text{ESA-Weeks} = 4 \times (\text{stop date} - \text{start date} + 1) / 7$.

The total number of ESA-week during the Treatment Period is calculated for each subject by the sum of the ESA-week between the analysis date of first dose and the analysis date of last dose for roxadustat only.

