**Table 3. Initial Dosing of Epoetin Alfa: Conversion table from Non-Epoetin ESAs to Epoetin Alfa**

Baseline ESA	Conversion Ratio	Examples of Converted Initial Epoetin Alfa dose (approximate) IU/week c
Epoetin (ie, alfa, beta, theta, zeta, delta, or omega) (IU/week) a	x 1	6,000 IU/week x 1 = 6,000 IU/week
Darbepoetin alfa (µg/week) a	x 200	40 µg/week x 200 = 8,000 IU/week
Mircera ® (µg/once monthly (ie, 4-wks) b	x 70 – 80 (for lower Mircera ® dose lower conversion ratio may be used) d	100 µg/month x 70 = 7,000 IU/week  200 µg/month x 80 = 16,000 IU/week

Abbreviations: ESA = erythropoiesis-stimulating agent; IU = international units.

- a Mean weekly ESA in 4 weeks prior to randomization
- b Mean monthly (4-week) ESA in 8 weeks prior to randomization
- c May be rounded as deemed necessary by the investigator
- d Per discretion of the investigator

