3.2 Rescue Therapy & Emergency Procedures

Red Blood Cell Transfusion (for all subjects):

For subjects in both treatment groups, red blood cell (RBC) transfusion is allowed if rapid correction of anemia is required to stabilize the subject's condition (e.g. acute hemorrhage) or the investigator is of the opinion that the blood transfusion is a medical necessity. Study treatment may continue during or after RBC transfusion administration.

ESA use:

For subjects randomized to roxadustat the use of ESAs is generally prohibited. ESA rescue is restricted to no more than one 4-week cycle of use during the Treatment Period; the Investigator may initiate use of an approved epoetin (EPO) analogue if all of the following criteria are met:

- A subject's hemoglobin level has not sufficiently responded to two or more dose increases or the maximum dose limit of the study drug has been reached; and
- The subject's hemoglobin is < 8.5 g/dL on two consecutive measurements (central lab) drawn at least five days apart; and
- Clinical judgment does not suggest iron deficiency or bleeding as a cause of lack of response or rapid decline in hemoglobin; and
- Reducing the risk of alloimmunization in transplant eligible patients and/or reduction of other RBC transfusion-related risks is a goal

The subject is not allowed to be administered both the EPO analogue and roxadustat at the same time. Treatment with an EPO analogue should be started ≥ 3 days after the last dose of roxadustat, and should be stopped when hemoglobin > 9 g/dL or after a 4-week cycle has been completed, whichever comes first. If a subject requires longer than 4-week therapy due to inadequate response, the Medical Monitor should be contacted. Study treatment should be resumed after the following intervals:

- Two days after stopping epoetin
- One week after stopping darbepoetin alfa
- Two weeks after stopping methoxy polyethylene glycol-epoetin beta (Mircera[®])

If more than one cycle of EPO analogue rescue is required, the Investigator should permanently discontinue roxadustat. Use of EPO analogues will be recorded in the eCRF. Roxadustat subject who receives an ESA inadvertently and does not meet the criteria above may be allowed to continue taking study medication, if considered safe by the Investigator or Medical Monitor.

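### The ESA-week formula multiplies elapsed weeks by 2 for darbepoetin and 4 for Mircera, so the listed total is wrong for these agents whether an entry is a course or a single dose (minor: descriptive listing only)

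*SAP*

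**What the plan says.** SAP 11.3.3.2 covers ESA use in the roxadustat arm. It states that "The total number of ESA-week dose per subject will be calculated and listed". The unit of calculation is the recorded entry: "For each entry that meets the criteria below the ESA-week will be calculated as follows". Three rules follow:

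- "If drug is epoetin alfa, epoetin beta, or an epoetin biosimilar (ATC code: B03XA01), then" the value is (stop - start + 1)/7.
- "If drug is darbepoetin SQ or IV dose (ATC code: B03XA02), then" the value is 2 × (stop - start + 1)/7.
- "If drug is Mircera IV or SQ dose (ATC code: B03XA03), then" the value is 4 × (stop - start + 1)/7.

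The section then adds the entries up: "The total number of ESA-week during the Treatment Period is calculated for each subject by the sum of the ESA-week", over the interval from first to last dose, for roxadustat subjects only.

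The section does not define an ESA-week, does not explain the 2 and the 4, and does not say whether an entry is one administration or a course. Elsewhere, the footnotes to SAP Table 1 foresee darbepoetin given every two weeks (the dose is halved to obtain a weekly figure) and average the Mircera dose over 4-week periods.

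**The concern.** The expression (stop - start + 1)/7 already yields weeks. The factors 2 and 4 coincide with a two-weekly darbepoetin interval and a four-weekly Mircera interval. An interval of that kind turns a number of doses into weeks covered; applied to a duration, it counts time twice over.

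All three agents can occur in the data. SAP 3.2 and Protocol 4.6.3.2 give a separate restart interval after each of them. Protocol 4.6.3.2 also lets roxadustat subjects continue after inadvertent or hospital-administered ESA.

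At stake is a descriptive figure. The US primary analysis keeps Hb values under rescue (Protocol 9.4.3.1, SAP 11.1.1.1), so a reader of the report may ask how much ESA the roxadustat arm received. The ESA-related rescue measures in SAP 4.3 are a proportion and a time to first use; ESA-weeks is the planned measure of amount.

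**Working it through.** Inputs: the multipliers m = 1, 2, 4 and the day count come from SAP 11.3.3.2. The 28-day length is the rescue cycle in SAP 3.2 ("ESA rescue is restricted to no more than one 4-week cycle of use during the Treatment Period"). The two-weekly and four-weekly intervals come from the footnotes to SAP Table 1. The SAP gives no worked ESA-week value to reproduce.

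Formula as written: ESA-weeks = m × (stop - start + 1)/7.

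| Agent | m | One 28-day entry | One single-day entry (start = stop) |
|---|---|---|---|
| Epoetin | 1 | 28/7 = 4 | 1/7 = 0.14 |
| Darbepoetin | 2 | 2 × 28/7 = 8 | 2/7 = 0.29 |
| Mircera | 4 | 4 × 28/7 = 16 | 4/7 = 0.57 |

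Two coherent definitions of an ESA-week are available.

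1. Calendar weeks on ESA. A 28-day entry should give 4 for every agent. The formula is 2 times too high for darbepoetin (8/4) and 4 times too high for Mircera (16/4).
2. Weeks covered by the doses given. One monthly Mircera dose should give 4. Entered as a single day it gives 0.57, too low by a factor of 4/(4/7) = 7. A two-weekly darbepoetin dose should give 2 and gives 0.29, again a factor of 7. A fixed factor of 2 would also not suit darbepoetin given weekly.

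The dependence on data entry is large. For Mircera, four weeks of cover is 0.57 as a single-day entry and 16 as a 28-day entry, a ratio of 16/(4/7) = 28. Two Mircera doses on Days 1 and 29, entered as one interval, give 4 × 29/7 = 16.6, against 2 × 4 = 8 weeks covered.

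Consistent dose-by-dose entry does not repair it. If epoetin is assumed to be given three times weekly, four weeks is 12 entries, 12 × 1/7 = 1.71. Two two-weekly darbepoetin doses give 2 × 2/7 = 0.57 and one Mircera dose gives 0.57. Mircera then counts one third as much as epoetin; entered as 28-day courses, it counts four times as much. The ordering of the agents reverses with the recording convention.

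**The case against.** The best case for leaving this alone is that little rests on it. The total is listed for one arm, with no model, test or between-arm comparison. It is not among the rescue endpoints in SAP 4.3, the fixed sequence in SAP Table 6 or the per-protocol exclusions in SAP Table 3. The influence of rescue on efficacy is handled elsewhere: the EU primary analysis sets Hb to missing after rescue (SAP 11.1.1.2), and SAP Table 5 includes a rescue-censored version of the US analysis. All of this stands, and it limits the point to a minor one.

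It can also be said that the 2 and 4 are nowhere called dosing intervals, so they might be a deliberate weighting, and that the 16 and the 0.57 require different ways of entering data. Both statements are correct. The interval reading is an inference from the matching figures in SAP Table 1 and from the rules' own reference to a dose. But a weighting is not stated, and it would not make 0.57 a sensible value for a monthly dose. Nor does either recording convention, taken alone, give a correct result for the long-acting agents.

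A reader might infer that a Mircera course scored as 16 would look like a breach of the 4-week rescue limit. The documents do not support that: the limit is set in cycles and calendar weeks, and nothing in the protocol or SAP judges it by ESA-weeks. A reader might also infer that comparisons between subjects are invalidated, but the SAP plans only a sum within each subject.

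**Conclusion.** The rule is wrong as written, not merely under-described. For darbepoetin and Mircera it matches neither calendar weeks nor weeks covered: it is 2 or 4 times too high on the first definition for a 28-day course, and 7 times too low on the second for a single administration. The listed total therefore depends on the agent and on how the site made the entry.

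The 8 and 16 assume a cycle entered as one 28-day interval; the 0.57 assumes start and stop on the same day. The SAP fixes neither.

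The consequence is confined to a descriptive listing. The primary analyses, the fixed-sequence tests and the definition of rescue are unaffected, so this is a minor correction. A reading in which efficacy conclusions are at risk is not supported.

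**What to change.** Define ESA-week in SAP 11.3.3.2, state whether an entry is a dose or a course, and replace the three lines with one consistent derivation.

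- Calendar weeks: (stop - start + 1)/7 for every agent, with no multiplier. A 28-day course then gives 4 throughout. This requires entries to be courses, since a single-day entry would still give 0.14.
- Weeks covered: (last administration date - first administration date)/7 plus one dosing interval for the agent as recorded. One monthly Mircera dose gives 0/7 + 4 = 4; doses on Days 1 and 29 give 28/7 + 4 = 8, and the same two doses entered separately give 4 + 4 = 8. The stop date must be defined as the date of the last administration: a single dose entered as Days 1 to 28 would otherwise give 27/7 + 4 = 7.9.

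Converting to summed epoetin-equivalent IU is a tempting substitute but does not work directly with the plan's ratios. SAP Table 2 and Protocol Table 3 convert Mircera per month into epoetin per week ("200 µg/month x 80 = 16,000 IU/week"), so that example corresponds to 4 × 16,000 = 64,000 IU over four weeks. Applying the ratio to each recorded monthly dose and summing would give 16,000. The ratio is also a range of 70 to 80.

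The cost is three formula lines and a small programming change. The weeks-covered version also needs administration dates and dosing intervals in the CRF. The documents say that ESA use is recorded but do not confirm those items, so this should be checked before choosing it.

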11.3.3.3 Use of Iron

IV Iron

Only IV iron therapy that started during the study treatment and up to the ET/EOT Visit will be taken into account for the total amount.

The average monthly IV iron use during weeks 53 to EOS will be calculated for monthly intervals. The Treatment Period will be divided in periods of 28 days and for each of these periods the monthly mean of IV iron will be used using the following formula:

Monthly iron use for each subject = $\text{Total IV iron in mg} / [(\text{last visit date} - \text{first dose date of study medication in the period} + 1) / 28]$

The following 2 endpoints will be analyzed:

- Proportion of subjects who receive IV iron. The proportion of subjects who received IV iron will be compared between the 2 treatments using logistic regression model adjusting for baseline iron repletion status and treatment group and stratification factors as fixed effects. (This will be performed for week 1 to week 36 as well).
- The average monthly iron use will be compared between the 2 treatment groups using ANCOVA model with baseline iron repletion status, and treatment group, and stratification factors as fixed effects.

Oral iron

The average monthly oral iron use during Weeks 28 to 52, and weeks 53 to ET/EOT will be calculated similarly to IV iron for monthly intervals.

The following 2 endpoints will be analyzed:

- Proportion of subjects who receive Oral iron. The proportion of subjects who received oral iron will be compared between the 2 treatment groups using logistic regression model adjusting for baseline iron repletion status, treatment group and stratification factors as fixed effects.
- The average monthly oral iron use will be compared between the 2 treatment groups using ANCOVA model with baseline iron repletion status, treatment group, and stratification factors as fixed effects.

In addition the proportion of subjects who received both IV and/or oral iron will be compared between the 2 treatments using logistic regression model adjusting for baseline iron repletion status and treatment group and stratification factors as fixed effects.

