During the Treatment Period, subjects will attend weekly study visits from Day 1 to Week 2, followed by every two weeks study visits from Weeks 4 to 24. Following Week 24, study visits will occur every four weeks until the End of Treatment (EOT). After EOT, subjects proceed to the post-treatment Follow-up Period and will return for the End of Study (EOS) visit. The schedule of assessments for the study is provided in Appendix 1.

All subjects discontinuing study medication prematurely will be followed up for vital status, cardiovascular events, and hospitalization until study closure, unless consent to participate is withdrawn. Upon completion of ET and 4-week Follow-up (EOS) visits, these subjects will be followed up every 3-6 month interval (depending on the availability of subjects) until study closure. These visits may occur either in-person or via telephone.

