Change from baseline in Hemoglobin from baseline to the average level during the Week 18 to 24 will be analyzed using the ANCOVA MI as the primary endpoints. Both Non-inferiority of roxadustat vs. Epoetin and superiority will be tested. The non-inferiority margin is fixed as a difference of -0.75.

11.2.2.4 Average Monthly of IV Iron Use during Weeks 28 to 52.

The average monthly IV iron use during Weeks 28 to 52 Treatment Period will be calculated for monthly intervals. The Treatment Period will be divided in periods of 28 days and for each of these periods the monthly mean of IV iron will be calculated using the following formula:

Monthly iron use for each subject = Total IV iron in mg / [(last visit date – first dose date of study medication +1)/ 28]

The average monthly iron use will be compared between the 2 treatment groups using An ANCOVA model with baseline iron repletion status, treatment group, and stratification factors as fixed effects. Superiority will be declared if the lower bound of the 2-sided 95% confidence interval of the difference between active control and roxadustat exceeds 0.

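### The Week 53 onward IV iron rate counts iron up to the ET/EOT visit but divides by time to an undefined last visit date

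*SAP*

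**What the plan says.** - **Numerator.** SAP 11.3.3.3 sets the limit: "Only IV iron therapy that started during the study treatment and up to the ET/EOT Visit will be taken into account".
- **Denominator.** The formula in the same section divides by the 28-day periods between "first dose date of study medication in the period" and the last visit date. No section defines that date.
- **Window.** "The average monthly IV iron use during weeks 53 to EOS will be calculated for monthly intervals". Protocol 3.2.3 also labels this summary to EOS. SAP 4.3 ends it at EOT (Weeks 53-104, then 105 to EOT). For oral iron, SAP 11.3.3.3 says "weeks 53 to ET/EOT will be calculated similarly to IV iron".
- **Ranked endpoint.** SAP 11.2.2.4, for Weeks 28 to 52, opens its formula with "Monthly iron use for each subject = Total IV iron in mg / [(last visit date" and subtracts the first dose date with no reference to the window. This endpoint is Test 4 in the fixed sequence (SAP Table 6), tested for superiority.
- **Off-drug follow-up.** SAP 3 schedules an EOS visit after EOT, and the schedule of assessments puts it 4 weeks later. Subjects who stop early are then contacted every 3 to 6 months until closure: "These visits may occur either in-person or via telephone". Protocol 4.6.2.2 allows IV iron in post-treatment follow-up.

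**The concern.** A rate per 28 days needs a numerator and a denominator over the same time. Here the iron stops counting at ET/EOT, while the clock, on a literal reading, runs on to a later visit. IV iron given after EOT is allowed but not counted, so those weeks can only lower the result. The loss is largest for subjects with little time on drug in the window. A summary of iron use per month on treatment would therefore partly measure how long subjects stayed on drug. IV iron use is a stated secondary objective and the trial is open-label, so the end date should be fixed in advance and not left to the programmer.

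**Working it through.** The documents state no monthly iron figure, so there is none to reproduce. The check takes a true rate of 100 mg per 28 days on drug in both arms (assumed) and asks what the formula returns.

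**1. One subject, Week 53 window.** Computed rate = 100 × on-drug weeks / (on-drug weeks + off-drug weeks to the last visit). The 4 weeks to EOS come from the schedule of assessments. The 26 and 52 weeks are assumed times to a long-term contact.

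| On-drug weeks in window | Last visit in Treatment Period | EOS, +4 weeks | +26 weeks | +52 weeks |
|---|---|---|---|---|
| 52 | 100 | 52/56 = 92.9 | 52/78 = 66.7 | 52/104 = 50.0 |
| 26 | 100 | 26/30 = 86.7 | 26/52 = 50.0 | 26/78 = 33.3 |
| 12 | 100 | 12/16 = 75.0 | 12/38 = 31.6 | 12/64 = 18.8 |
| 4 | 100 | 4/8 = 50.0 | 4/30 = 13.3 | 4/56 = 7.1 |

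**2. Arm means.** Assumed: completers have 52 on-drug weeks plus EOS (92.9), and discontinuers have 26 on-drug weeks. A discontinuer scores 86.7 under the EOS reading. With 30 off-drug weeks to a long-term contact, the score is 26/56 = 46.4. The discontinuation percentages are also assumed.

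- EOS, 30% v 20%: 0.7 × 92.9 + 0.3 × 86.7 = 91.0, against 0.8 × 92.9 + 0.2 × 86.7 = 91.6. Ratio 0.993.
- EOS, 40% v 20%: 90.4 against 91.6. Ratio 0.986.
- Long-term contacts counted, 30% v 20%: 0.7 × 92.9 + 0.3 × 46.4 = 78.9, against 0.8 × 92.9 + 0.2 × 46.4 = 83.6. Ratio 0.944.
- Long-term contacts counted, 40% v 20%: 74.3 against 83.6. Ratio 0.889.
- Equal discontinuation with the same timing: ratio 1.000 under every reading.

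**3. Ranked endpoint, SAP 11.2.2.4.** Suppose only iron from Weeks 28 to 52 counts. A completer has 24/4 = 6 periods × 100 = 600 mg. The literal denominator starts at first dose:

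- Last visit at Week 52: 600/13 = 46.
- Last visit at Week 104: 600/26 = 23.
- Last visit at Week 156: 600/39 = 15.

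Correcting only the end date leaves a completer at 46. A subject who stops at Week 32 has 4 countable weeks, or 100 mg, over 32/4 = 8 periods, giving 12.5. Correcting the start date as well gives 600/6 = 100 and 100/1 = 100.

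**The case against.** The strongest reply is that the SAP intends a denominator confined to treatment. SAP 11.3.3.3 says "The Treatment Period will be divided in periods of 28 days", and its formula refers to dates in the period. SAP 4.3 and the oral iron window stop at EOT or ET/EOT. Appendix 5 (16.5.3) lets the last visit date stand in for a missing last dose date. On that reading there is no dilution. It is a fair reading, so an off-drug denominator is not established as the plan's intent. But the SAP qualifies the term when it wants a treatment-bound date. The missing-dose rule in 16.5.1 specifies the last visit within the Treatment Period, and transfusion time at risk in 11.3.3.1 ends at last study medication. The IV iron formula has no such limit, and its window is named to EOS.

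The reply is stronger on long-term contacts. Although the SAP calls them visits, Table 11 excludes them from the final study visit. They collect only vital status, CV events and hospitalization. Subjects who die, withdraw consent or are lost will not have them through to closure. The lower figures in the table above therefore rest on the weakest reading.

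A reader might infer that extra stopping on roxadustat would manufacture part of an IV iron advantage. Protocol 4.6.3.2 does require permanent roxadustat discontinuation when more than one ESA rescue cycle is needed, and states no matching rule for epoetin alfa. That makes unequal stopping conceivable, but it supplies no rates and does not show which arm stops more overall. The Week 53 summary is also outside the fixed sequence, and the ET/EOT limit on the numerator is written only in 11.3.3.3. Carrying it to 11.2.2.4 is an inference.

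**Conclusion.** The mismatch in SAP 11.3.3.3 is real as written: two end dates sit in one rate, one of them undefined, and the window label conflicts with two other places in the SAP. Followed literally, and assuming subjects attend EOS, the rule understates the on-drug rate by about 7% for 52 on-drug weeks and 25% for 12.

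A material bias between arms is not established. It needs unequal or differently timed stopping, which the documents do not quantify. In these illustrations it stays near 1% unless long-term contacts are also taken as the last visit. Neither its direction nor a spurious roxadustat benefit can be stated. Oral iron inherits the formula, but its window already ends at ET/EOT.

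For the ranked endpoint the start date matters more. Read literally with a Weeks 28 to 52 numerator, a completer whose last visit is Week 52 scores less than half the true rate. If total iron there instead means all iron since first dose, the result is not a Weeks 28 to 52 rate. The correction is worth making because the formula feeds a ranked superiority test and costs almost nothing to repair.

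**What to change.** In SAP 11.2.2.4 and 11.3.3.3, define one interval per subject and window and use it for both the iron counted and the time divided by. It runs from the later of first dose and the window start to the earlier of the ET/EOT visit and the window end. Apply it to oral iron too.

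Change the 11.3.3.3 IV iron label from Weeks 53 to EOS to Weeks 53 to EOT, and reconcile it with SAP 4.3. Since Protocol 3.2.3 uses the EOS label, record the change in the SAP. State how subjects who stop before a window opens are handled, because their interval is empty.

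The cost is SAP wording and one derivation line, with no new data. With equal true use on drug, the corrected rate is 100 mg per 28 days for every subject with time in the window, and the arm ratio is 1.000 at any discontinuation rate.
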